## **8.4 Vital signs, physical findings, and other observations related to safety**

### **8.4.1 Vital signs, body weight, height, and BMI**

Vital signs (systolic blood pressure [SBP], diastolic blood pressure [DBP], pulse rate, and temperature), body weight, and height will be collected according to the tabular schedule of study procedures. In addition, BMI will be calculated (as defined in Section 3.2.11) for each visit where weight and height are collected.

Noninvasive blood pressure (systolic and diastolic) and pulse rate will be measured at all visits in a sitting position after at least 3 minutes at rest. Body weight will be determined without shoes and wearing light clothing. Height will be measured without shoes.

All summaries of vital signs, body weight, height, and BMI will only summarize variables planned based on the protocol. However, both planned and unplanned variables will be provided in subject data listings.

Observed values of SBP, DBP, pulse rate, temperature, body weight, height, and BMI will be summarized for each visit and Last Visit. Change from Baseline for SBP, DBP, pulse rate, temperature, body weight, height, and BMI will be summarized for all post-Baseline visits, and Last Visit.

Markedly abnormal (MA) values are defined as those MA values during the defined Treatment Period at scheduled or unscheduled visits which occur on or after the first SP848 LCM administration through to the end of the study.

The number and percentage of study participants with a MA value, MA low value, and MA high value, at each post-Baseline visit and Last Visit, for which SBP, DBP, pulse rate, temperature, and body weight were scheduled to be assessed, and Last Visit, will be presented. Percentages will be relative to the number of study participants with a value at each time point.

The abnormal vital sign criteria are defined as follows:

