### 3.2.7 Exposure duration

The overall duration of LCM exposure for each subject will be calculated as the date of the last dose of LCM minus the date of the first dose of LCM plus 1 day. Gaps in treatment or days with unknown dosing will not be subtracted from the duration of exposure. The duration of LCM exposure will be summarized, separately, as a continuous parameter (in days) and as a categorical parameter, where categories will be defined using the following cumulative 6-month intervals for the Treatment Period: >0 months, >6 months, >12 months, >18 months, >24 months, >30 months, >36 months, >42 months, and >48 months.

Subject-years of LCM exposure in the study is calculated as the duration of exposure (days) divided by 365.25. Subject-years of LCM exposure will be summarized using the following cumulative 6-month time intervals for the Treatment Period: >0 months, >6 months, >12 months, >18 months, >24 months, >30 months, >36 months, >42 months, and >48 months, where 1 month is defined as 28 days.

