### **3.3 Definition of Baseline values**

In general, Baseline will be defined as the last non-missing value collected prior to the first dose of LCM in the original study for rollover subjects and in SP848 for direct enrollers for safety and efficacy variables unless otherwise noted for a specific type of data. The Baseline value for seizure counts for directly enrolled study participants will be taken from the Historical Seizure Count CRF/eCRF module collected in SP848 in combination with the seizure diary data collected from the date of the Screening Visit to the day prior to the date of first dose of LCM.

For participants enrolling from EP0060 the baselines for the questionnaires will consider each EP0060 enrollment group separately, those are: ILL (Initiating intravenous lacosamide Group: not currently receiving LCM, i.e. LCM naïve), OLL (Open-label lacosamide Group: currently receiving oral LCM in open-label long term study), and RxL (Prescription lacosamide Group: currently receiving prescribed oral LCM from commercial supply, VIMPAT). For ILL group baseline will be Visit 1 from SP848, for OLL group baseline will come from SP848 using above baseline definition, and for RxL group there will be no baseline data as they were on oral LCM prior to EP0060.

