### 8.3 Clinical laboratory evaluations

Hematology, blood chemistry (including liver function tests), urinalysis, and endocrinology parameters are assessed throughout the study, according to the tabular schedules of study procedures. Urinalysis will be performed for study participants  $\geq 5$  years of age only.

All summaries of laboratory parameters will only summarize parameters planned based on the protocol. However, both planned and unplanned laboratory parameters will be provided in subject data listings. Summaries will include hematology, chemistry and endocrinology results; urinalysis results will be included in subject data listings only.

Observed values of hematology, chemistry, and non-gender specific endocrinology parameters (ie, thyroid stimulating hormone, triiodothyronine [total and serum-free], and thyroxine [total and serum-free]) will be summarized for each visit and Last Visit. Change from Baseline for hematology, chemistry, and non-gender specific endocrinology parameters will be summarized for all post-Baseline visits, and Last Visit. Gender specific endocrinology parameters (ie, follicle stimulating hormone, luteinizing hormone, and testosterone) will be presented similarly, by gender.

A shift table that cross-tabulates Baseline versus maximum result during the Treatment Period in categories of  $<1 \times \text{ULN}$  (upper limit of normal),  $1$  to  $<2 \times \text{ULN}$ ,  $2$  to  $<3 \times \text{ULN}$ ,  $\geq 3 \times \text{ULN}$ , and missing will be presented for liver function tests (LFT) which include Alanine Aminotransferase (ALT), Aspartate Aminotransferase (AST), Gamma-glutamyl Transferase (GGT), Total Bilirubin, and Alkaline Phosphatase.

Treatment-emergent markedly abnormal (TEMA) values are defined as those TEMA values during the defined Treatment Period at scheduled or unscheduled visits which occur on or after the first SP848 LCM administration through to the end of the study but were normal at Baseline. The age at the time of assessment will be used for determining TEMA. The age at the time of visit/assessment will be obtained using date of informed consent to date of visit.

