**Table 8–1: Vital signs abnormality criteria**

Parameter	Age Range	Abnormality Criteria
Diastolic Blood Pressure (mmHg)	<6m	<40 >65
	6m - <3y	<45 >75
	3y - <12y	<50 >80
	12y - <17y	≤50 ≥105
	≥17y	≤50 and a decrease from Baseline of ≥15 ≥105 and an increase from Baseline of ≥15
Temperature	>1m	>101 °F (38.3 °C)
Body Weight	1m - <17y	<3% or >97% of the normal body weight growth curve ranges a based on gender and the age of subject on date of weight assessment
	≥17y	≥10% change from Baseline (an increase or a decrease)

Abbreviations: m=months, y=years. A month is defined as 28 days; a year is defined as 365.25 days.

a Source: <http://www.cdc.gov/growthcharts/>.

A subject data listing of all vital signs for study participants with an AE mapped to the PT bradycardia or sinus bradycardia will be presented.

A subject data listing of all vital sign values including body weight, height, and BMI for all study participants will be presented. A separate listing including MA vital signs values will also be presented.

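### Weight, height and BMI are summarized only as raw change, and the markedly abnormal weight counts mix in pre-existing status and, from age 17, possible ordinary growth, so the tables are a poor guide to growth deviation.

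*SAP*

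**What the plan says.** Section 8.4.1 plans observed values and raw change by visit and at Last Visit: "Change from Baseline for SBP, DBP, pulse rate, temperature, body weight, height, and BMI will be summarized for all post-Baseline visits". No z-score, percentile change or growth velocity appears anywhere in the SAP. Section 3.1 sets the default age groups for these tables, by age at entry into SP848: 1 month to under 4 years, 4 to under 18 years, and 18 or over, plus totals.

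MA counts are planned at post-Baseline visits and Last Visit, "for which SBP, DBP, pulse rate, temperature, and body weight were scheduled to be assessed". Height and BMI are not in that list and have no criterion in Table 8–1. For weight, Table 8–1 gives two rules:

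- from 1 month to under 17 years, "<3% or >97% of the normal body weight growth curve ranges", read by sex and by age on the day of weighing, with a published growth reference cited in the footnote;
- from 17 years, "≥10% change from Baseline (an increase or a decrease" being the wording of a raw-change rule in either direction.

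The MA definition carries no condition on Baseline status: "Markedly abnormal (MA) values are defined as those MA values during the defined Treatment Period at scheduled or unscheduled visits". The laboratory definition in section 8.3 does, covering values "through to the end of the study but were normal at Baseline". The ECG definition in section 8.4.2 likewise excludes criteria already met at Baseline.

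Baseline (section 3.3) is the "last non-missing value collected prior to the first dose of LCM in the original study for rollover subjects", and the pre-dose value in SP848 for direct enrollers. Exposure categories in section 3.2.7 extend to ">30 months, >36 months, >42 months, and >48 months".

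**The concern.** Children as young as 1 month are followed without a control group. A mean gain in kg or cm is what any group of children would show, and its size depends on the ages in the band and the time elapsed. A reader of the change tables has nothing to set it against.

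The MA weight counts are the only planned summary that compares a body measurement with an age norm. Under 17 years they record where a child stands at a visit, not whether the child has moved since starting lacosamide. From 17 years they record movement, but without allowing for age or elapsed time. The SAP treats growth as a topic of interest, since section 8.2 plans a separate table of growth-related TEAEs. What is at stake is whether the body-measurement tables can support or question what that table shows.

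**Working it through.** The SAP gives no precision or power figure for growth and plans no test, so there is no figure to reproduce. The check is on how the rules behave. Growth rates, correlations and drift sizes below are assumptions shown as ranges; the SAP gives none.

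**1. Raw change.** Assume normal height growth of 4 to 8 cm a year and a deficit of 1 cm a year, over 2 years.
- Normal: 2 × 4 = 8 cm to 2 × 8 = 16 cm.
- With deficit: 2 × (4 − 1) = 6 cm to 2 × (8 − 1) = 14 cm.

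The ranges overlap from 8 to 14 cm. In a band from 4 to under 18 years, a deficit of this size cannot be told from a different age mix.

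**2. Weight flag under 17 years.** Reading the limits as the 3rd and 97th percentiles, z = ±1.881.
- Reference population, no drug effect: 3.0% low + 3.0% high = 6.0% at every visit.
- Share of flagged participants who already met the flag at Baseline, from a bivariate normal simulation (2,000,000 draws): 45%, 60% and 72% at Baseline-to-visit correlations of 0.80, 0.90 and 0.95.
- Uniform drift of −0.5 SD: low flags Φ(−1.881 + 0.5) = 8.4%, high flags 0.9%.
- A child moving from the 50th percentile to the 16th (−1 SD) or the 7th (−1.5 SD) is not flagged, because neither passes −1.881.

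If a flag had to be new since Baseline, the low rate with no drug effect would be 1.6%, 1.2% and 0.8% at the three correlations. Under the −0.5 SD drift it would be 6.1%, 5.7% and 5.4%.

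**3. Weight flag from 17 years.** Under steady compound gain g, the limit is reached after ln(1.10)/ln(1 + g) years.

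| Assumed gain per year | Years to +10% |
|---|---|
| 3% | 3.22 |
| 5% | 1.95 |
| 8% | 1.24 |

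In reverse, the gain needed is 1.10^(1/t) − 1: 4.9% a year over 2 years, 3.2% over 3 years, and 2.6% over 48 months of 28 days (48 × 28/365.25 = 3.68 years). A participant who simply fails to gain weight is never flagged by this rule.

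**The case against.** Much can be said for the plan as written.

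- A reader might infer that the weight flags in general fire on normal growth. They do not. The rule under 17 years is already normed for age and sex; its weakness is pre-existing status. Only the rule from 17 years can respond to normal growth, and it touches the oldest edge of a population that enters at up to 18 years (section 2.4.1.2).
- A reader might infer that the study cannot show a growth effect at all. That is too strong. MA low and MA high are counted separately, so the low rate can be set against a nominal 3%. That gives a coarse, age-adjusted signal, provided the cohort matched the reference at Baseline, and no Baseline MA rate is planned to check this.
- A reader might also infer that most MA weights are non-events. The 45% to 72% range depends wholly on assumed correlations, and at 0.80 it is under half.
- Direct enrollers are treated for up to 2 years, and section 3.2.3 names only Japanese sites as allowed longer. Over 2 years the 3% case never reaches the limit and the 5% case only just does. Against this, rollover Baselines lie in the parent study, which lengthens the interval.
- Weight, height and BMI are listed as other safety variables, the SAP is descriptive, and growth is also covered by the TEAE table, the Tanner stage shift, endocrinology and full listings.
- Different rules for vital signs and laboratory values are not a contradiction; the MA definition is uniform across Table 8–1.

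These points limit the claim but do not remove it. The TEAE table depends on reported events and medical review, and the Tanner shift measures puberty. None of the other outputs summarizes deviation from expected growth.

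**Conclusion.** The point holds in limited form. Raw mean changes in wide age bands are a poor guide to growth deviation. The MA weight counts add only coarse information: under 17 years they include participants already outside the limits at Baseline, with about 3% low and 3% high expected without any drug effect; from 17 years they may flag ordinary growth when Baseline was taken before that age. The second fault matters most for rollovers and for participants followed beyond 2 years, with times to the limit of 3.2, 2.0 or 1.2 years at assumed gains of 3%, 5% or 8% a year.

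The 6% total follows from the percentile limits in a reference population. How many flags were present at Baseline, and how often the 10% rule fires on normal growth, depend on the assumptions above. No primary or secondary variable is affected. Nor would better summaries isolate a drug effect: in a single arm, even standardized scores leave lacosamide mixed with disease and concomitant antiepileptic drugs.

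**What to change.** In section 8.4.1 and Table 8–1:

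1. Beside the raw values, summarize observed value and change from Baseline in age- and sex-standardized z-scores for weight, height and BMI. Use the growth reference already cited under Table 8–1, after confirming which parameters and ages it covers, since the SAP cites it only for weight. Mean z-score change is zero under normal growth for a cohort that follows the reference, so a drift would show directly.
2. Report MA weight as treatment-emergent (same criterion not met at Baseline), or show the Baseline MA rate beside the post-Baseline counts. The second option keeps one MA definition for all of Table 8–1.
3. Apply the 10% rule only to participants aged 17 or over at Baseline. Keep the percentile criterion for the others as far as the reference covers their age.

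The cost is SAP wording and programming. The data are already collected, the under-17 rule already requires each weight to be placed by age and sex, and no visit or assessment is added.

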**Table 8–1: Vital signs abnormality criteria**

Parameter	Age Range	Abnormality Criteria
Pulse Rate (beats/minute)	<6m	<100 >180
	6m - <3y	<90 >150
	3y - <12y	<60 >130
	12y - <17y	≤50 ≥120
	≥17y	≤50 and a decrease from Baseline of ≥15 ≥120 and an increase from Baseline of ≥15
Systolic Blood Pressure (mmHg)	<6m	<60 >100
	6m - <3y	<70 >120
	3y - <12y	<80 >140
	12y - <17y	<90 >160
	≥17y	≤90 and a decrease from Baseline of ≥20 ≥180 and an increase from Baseline of ≥20

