The number and percentage of study participants with treatment-emergent ECG abnormalities will be presented for each post-Baseline visit and Last Visit. Abnormalities reported at an unscheduled visit will be summarized under the scheduled visit preceding the unscheduled visit (if the abnormality was not present already at the preceding scheduled visit). Treatment-emergent is defined as meeting the criteria at any post-Baseline visit during the Treatment Period (including unscheduled visits) and not meeting the same criteria during Baseline. The age at the time of visit/assessment will be used for determining abnormality criteria. The age at the time of assessment will be obtained using date of informed consent to date of visit. All ECG parameter values will be listed for study participants meeting any abnormality criteria.

Abnormality criteria to be used in the determination of ECG abnormalities are defined as follows, where increase and decrease are relative to Baseline values:

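### Under 17 years, markedly abnormal counts for pulse and blood pressure have no Baseline condition and no Baseline row, so these tables cannot separate new from pre-existing abnormality

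*SAP*

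**What the plan says.** SAP 8.4.1 gives the definition: "Markedly abnormal (MA) values are defined as those MA values during the defined Treatment Period at scheduled or unscheduled visits", on or after the first SP848 dose. That is a condition on timing and nothing else. The table to be produced is "The number and percentage of study participants with a MA value, MA low value, and MA high value, at each post-Baseline visit", and the time points are those "at each post-Baseline visit and Last Visit, for which SBP, DBP, pulse rate, temperature, and body weight were scheduled to be assessed". On the denominator: "Percentages will be relative to the number of study participants with a value at each time point". It therefore includes participants who were already abnormal at Baseline.

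The limits are in Table 8–1. For pulse, SBP and DBP the four bands below 17 years are absolute limits only. The ≥17 years rows add a change from Baseline, for example "≤50 and a decrease from Baseline of ≥15 ≥120 and an increase from Baseline of ≥15" for pulse and "≤90 and a decrease from Baseline of ≥20 ≥180 and an increase from Baseline of ≥20" for SBP.

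Two neighbouring sections treat Baseline differently. Section 8.3 counts a laboratory value as treatment-emergent only if the Baseline value was normal. Section 8.4.2 counts an ECG abnormality as treatment-emergent only when it is met after Baseline while "not meeting the same criteria during Baseline".

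**The concern.** A participant under 17 whose pulse or blood pressure lay outside the limit before any lacosamide, and has not moved, enters the MA count at every visit where the value persists. No Baseline MA percentage is tabulated, so the post-Baseline percentages have no reference within the table. The study has one arm, so no control group can supply one.

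What is at stake is how the table reads. A row showing some percentage of children with low DBP at a visit could be all pre-existing, all new or any mixture, and the table cannot say which. The ≥4 to <18 years column also pools children counted on level alone with 17-year-olds counted on level plus change.

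**Working it through.** The SAP states no figure on this point, so there is none to reproduce. The check sets the rules side by side, applies them to unchanged values, and then gives an illustration.

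**1. Which rules use Baseline**

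| Rule | Baseline used? |
|---|---|
| Pulse, SBP, DBP, all four bands <17y (Table 8–1) | No |
| Pulse, SBP, DBP, ≥17y (Table 8–1) | Yes: change of ≥15, ≥20, ≥15 |
| Temperature (Table 8–1) | No |
| Body weight <17y (Table 8–1) | No (growth-curve percentile) |
| Body weight ≥17y (Table 8–1) | Yes: ≥10% change |
| Laboratory TEMA (8.3) | Yes: normal at Baseline |
| Treatment-emergent ECG, including heart rate (8.4.2) | Yes: criterion not met at Baseline |

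**2. Post-Baseline value equal to Baseline**

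- Age 8, pulse 55 at Baseline and at the visit: the limit is <60, so MA low.
- Age 14, SBP 85 at both: the limit is <90, so MA low.
- Age ≥17, any value: the change is 0, which is below 15 or 20, so never MA.

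Coding the three parameters and applying them to whole-number values confirmed this. Every unchanged value outside the limits is flagged in each band under 17, and none is flagged at ≥17 years.

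**3. Overlap with ECG heart rate**

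In the three bands below 12 years, the heart-rate limits in Table 8–2 equal the pulse limits in Table 8–1: <100/>180, <90/>150, <60/>130. From 12 years, Table 8–2 has <50/>120, against ≤50/≥120 for pulse at 12 to <17 years. The ECG table excludes criteria already met at Baseline. The same child with the same unchanged rate is thus left out of one table and counted in the other. Blood pressure has no such counterpart.

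**4. Illustration of size, with no drug effect**

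Inputs, all assumed and none from the SAP: proportion q outside a one-sided limit at any visit; correlation r between Baseline and visit; bivariate normal values.

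- Limit: c = Φ⁻¹(1 − q).
- MA at both times: B = 1 − 2(1 − q) + Φ₂(c, c; r).
- Tabulated MA rate: q. Newly MA: q − B. Share of flags already MA at Baseline: B/q.

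For q = 0.05 and r = 0.7: c = 1.645 and B = 0.0196. Newly MA = 0.05 − 0.0196 = 0.0304. Share = 0.0196/0.05 = 39%.

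| q | r = 0.4 | r = 0.5 | r = 0.7 | r = 0.8 |
|---|---|---|---|---|
| 2% | 12% | 17% | 31% | 42% |
| 5% | 19% | 24% | 39% | 50% |
| 10% | 27% | 32% | 47% | 56% |

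Cells are B/q. With no drug effect and the same q at both times, the chance that a child abnormal at Baseline is flagged at the visit is also B/q. It is the same quantity, not a second finding.

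**5. Age-band crossing**

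Section 8.4.1 does not say which age selects the pulse or blood-pressure band at a visit; 8.3 and 8.4.2 use age at assessment. If age at assessment is used here too, an unchanged value can go from not MA to MA on a birthday:

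- pulse 131–150 at the 3rd (limit >150 becomes >130);
- SBP 70–79 at the 3rd (<70 becomes <80);
- pulse 120–130 at the 12th (>130 becomes ≥120);
- SBP 80–89 at the 12th (<80 becomes <90).

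A treatment-emergent rule that judged Baseline by Baseline-age limits would call these values new.

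**The case against.** The strongest reply is that the SAP keeps MA and TEMA as separate terms and uses MA for vital signs. The table claims only that a value occurred on treatment, which is a legitimate descriptive choice. That stands as a defence of the label. It does not supply the missing Baseline reference.

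Several stronger readings are tempting but unsupported:

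- A reader might infer that nothing in the output shows whether pulse or blood pressure changed. Section 8.4.1 plans observed values and change from Baseline by visit, a full listing and a separate MA listing, so individuals can be traced. What is missing is a tabulated count of children who became abnormal.
- A reader might infer that these are the only rules without a Baseline condition. Temperature and under-17 body weight lack one too.
- A reader might infer that a Baseline condition would isolate a drug effect. It would not. In the illustration, 44–88% of flags remain after pre-existing cases are removed, with no drug effect at all.
- A reader might infer that a true signal is shown to be diluted. No drug effect was modelled, so that has not been shown.

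It is also fair to say that vital signs are other, not primary, safety variables, that nothing is tested, and that criteria differing at 17 years also occur in the ECG and laboratory tables. These points limit the importance but leave the gap in place.

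**Conclusion.** The point holds for the MA tables for pulse, SBP and DBP under 17 years: they cannot distinguish newly abnormal values from values already abnormal at Baseline. This follows from the text of 8.4.1 and Table 8–1 and needs no assumption. It matters most for blood pressure, since heart rate has a Baseline-conditioned count wherever ECGs are taken.

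The size is not known from the SAP. The 12–56% range depends wholly on the assumed prevalence (2–10%), correlation (0.4–0.8) and normal model. This is an inexpensive improvement to interpretability; it does not make the safety analysis invalid.

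**What to change.** In 8.4.1:

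1. Keep the all-MA table and add a Baseline row (n, %).
2. For pulse, SBP and DBP, add either a Baseline-to-post-Baseline shift table or a treatment-emergent MA low/high count: criterion met after Baseline, same-direction criterion not met at Baseline, as in 8.4.2. The ≥17 years rows are unaffected, because a Baseline value cannot differ from itself.
3. State that age at assessment selects the band, and that the same visit-age limits are applied to the Baseline value. An unchanged value is then not called new when a child crosses a band.
4. State the denominator for the treatment-emergent count: participants with a value at the visit and a Baseline value not meeting the criterion. Show participants without a Baseline value on a separate line.

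The cost is SAP wording, one derived flag, and one extra row or table. Denominators become slightly smaller. Section 3.3 already defines Baseline for rollover participants and direct enrollers, so no new data are needed.
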